3.6 Dose-limiting Toxicities

For the purpose of guiding dose escalation, DLTs will be defined based on the incidence and grade of AEs for which no alternate cause can be identified (Section 4.3.1). The incidence of DLTs which occur within 4 weeks following the start of study therapy will guide dose escalation decisions. AEs will be graded according to the National Cancer Institute (NCI) Common Terminology Criteria for Adverse Events version 4.03 (CTCAE v4.03). For the purposes of subject management, drug-related AEs occurring at any time which meet the DLT definition will lead to dose interruption and/or permanent discontinuation of study drug as defined in Section 4.3.6.

[figure not shown]
The DLT evaluation interval begins on the first day of treatment and continues for 4 weeks, that is, through Day 28 of the first cycle in both Parts A and B. Subjects discontinued during DLT observation period due to DLT are also considered as DLT evaluable. Based on the predicted human T-HALF of BMS-986156 of 2 weeks, this interval is expected to cover the anticipated time frame for the occurrence of clinically significant immediate and early onset AEs related to (i) single dose BMS-986156 monotherapy or first combination dose with nivolumab and, (ii) repeat dosing of monotherapy BMS-986156 as well as combination dose with nivolumab.

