3.11 Discontinuation of Subjects Following Any Treatment with Study Drug

Subjects MUST discontinue investigational product (IP) (and non-IP at the discretion of the Investigator) for any of the following reasons:

- Subject's request to stop study treatment and/or participation in the study
- Any clinical AE, laboratory abnormality or intercurrent illness which, in the opinion of the Investigator, indicates that continued participation in the study is not in the best interest of the subject
- Termination of the study by BMS
- Loss of ability to freely provide consent through imprisonment or involuntarily incarceration for treatment of either a psychiatric or physical (e.g., infectious disease) illness
- Pregnancy

- Documented and confirmed disease progression as defined by RECIST (see [Appendix 3](#)) unless subject meets criteria for treatment beyond progression (Section 3.11.1)
- Clinical deterioration while receiving active study therapy that in the opinion of the Investigator indicates that continued participation in the study is not in the best interest of the subject
- Discretion of the Investigator
- Inability to comply with the protocol requirements
- Protocol defined reasons for discontinuation (see [Section 4.3.6](#)).

In the case of pregnancy, the Investigator must immediately notify the BMS Medical Monitor/Designee of this event. In most cases, the study drug will be permanently discontinued in an appropriate manner. If the Investigator determines a possible favorable benefit/risk ratio that warrants continuation of study drug, a discussion between the Investigator and the BMS Medical Monitor/Designee must occur.

All subjects who discontinue IP should comply with protocol specified follow-up procedures as outlined in [Section 3.3](#). The only exception to this requirement is when a subject withdraws consent for all study procedures including post-treatment study follow-up or loses the ability to consent freely (e.g., is imprisoned or involuntarily incarcerated for the treatment of either a psychiatric or physical illness).

If study drug is discontinued prior to the subject's completion of the study, the reason for the discontinuation must be documented in the subject's medical records and entered on the appropriate CRF page.

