4.3.1 Dose-limiting Toxicities

AEs will be graded according to the NCI CTCAE v4.03.

Non-hematologic Dose-limiting Toxicity (DLT)

A. Hepatic Non-hematologic DLT

Any one of the following study drug-related events will be considered a hepatic DLT:

- Any Grade ≥ 3 elevation of AST, ALT, or total bilirubin
- Grade 2 AST or ALT with symptomatic liver inflammation (e.g., right upper quadrant tenderness, jaundice, pruritus)
- AST or ALT $> 3 \times$ ULN and concurrent total bilirubin $> 2 \times$ ULN without initial findings of cholestasis (elevated serum ALP (e.g., findings consistent with Hy's law or FDA definition of potential drug-induced liver injury or pDILI). Note that this special category of DLT uses ULN rather than CTC Grade for definition

B. Non-hepatic Non-hematologic DLT

Any of the following events will be considered a Non-Hepatic Non-Hematologic DLT:

- Any Grade 2 drug-related uveitis or eye pain or blurred vision that does not respond to topical therapy and does not improve to Grade 1 severity ≤ 2 weeks OR requires systemic treatment
- Grade 3 drug-related uveitis, pneumonitis, bronchospasm, neurologic toxicity, hypersensitivity reaction, or infusion reaction of any duration requires discontinuation
- Any Grade 3 or greater non-dermatologic, non-hepatic non-hematologic study drug-related toxicity will be considered a dose-limiting toxicity with the following specific EXCEPTIONS:
 - Grade 3 or grade 4 electrolyte abnormalities that are not complicated by associated clinical adverse experiences, last ≤ 48 hours and either resolve spontaneously or respond to conventional medical intervention
 - Grade 3 nausea, vomiting or diarrhea that lasts less than 48 hours, and either resolves spontaneously or responds to conventional medical intervention
 - Isolated Grade 3 elevation of amylase or lipase not associated with clinical or radiographic evidence of pancreatitis
 - Isolated Grade 3 fever not associated with hemodynamic compromise (eg, hypotension, clinical or laboratory evidence of impaired end-organ perfusion)
 - Grade 3 endocrinopathy that is well controlled by hormone replacement
 - Grade 3 tumor flare (defined as pain, irritation, or rash that localizes to sites of known or suspected tumor)
 - Grade 3 fatigue for ≤ 7 days
 - Grade 3 infusion reaction that returns to Grade 1 in ≤ 6 hours

C. Dermatologic DLT

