4.3.4 Dose Delays Due to Toxicity

Subjects who experience a DLT must have study drug held. Subjects who are required to permanently discontinue both study drugs are listed in [Section 4.3.6](#). In addition, all Grade 2 hepatic, pulmonary, renal, gastrointestinal, and neurological AEs should be evaluated and managed per the toxicity management algorithms ([Appendix 4](#)). Subjects not meeting guidelines for permanent discontinuation will be permitted to resume therapy based on the criteria specified below in [Section 4.3.5](#). Subjects eligible to resume study therapy will resume study therapy at the treatment visit following their last received study medication dose.

In Parts A and C, if there is a delay in dosing of BMS-986156 of between 1 -12 days, the procedures at the original scheduled visit should be performed as soon as possible. If the delay is more than

12 days, the visit and dose will be considered missed; the procedures at the next scheduled visit should be performed, and subsequent BMS-986156 doses will follow every 2 weeks.

In Parts B, D and E depending on the dosing schedule (See [Table 5.1-2](#)), if there is a delay in dosing of combination dose (same day dose of BMS-986156 and nivolumab) of between 1 -12 days, If the delay is more than 12 days, the visit and dose will be considered missed; the procedures at the next scheduled visit should be performed, and subsequent combination doses will follow after 2 weeks.

Extensions to the period of dose delays may be granted for individual subjects on a case by case basis after specific consultation and agreement between the Investigator and BMS Medical Monitor in settings where benefit/risk may justify continued study therapy (e.g., subject deriving clinical benefit who requires prolonged steroid taper for management of non-DLT drug-related AEs, or experiences delays for management of a non drug related AE).

The end of cycle tumor assessments (i.e., CT/MRI, positron emission tomography, etc) will continue on an every 8 weeks schedule relative to the subject's 1st dose regardless of any treatment delay incurred.

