4.3.6 Guidelines for Permanent Discontinuation

Subjects will be required to permanently discontinue both study drugs for the following AEs:

- Any drug related AE occurring at any time that meets DLT criteria as outlined in [Section 4.3.1](#) will require permanent discontinuation with the following **exceptions**:
 - a) Grade 3 diarrhea, nausea, vomiting, or abdominal pain that returns to grade 1 or baseline within 3 days with medical intervention;
 - b) Grade 3 pruritus or rash that returns to grade 1 or baseline within 7 days or baseline with medical intervention;
 - c) Grade 4 electrolyte abnormalities that \leq 72 hours in duration;
 - d) Grade 4 neutropenia \leq 5 days in duration;
 - e) Grade 4 increase in amylase or lipase that is not associated with clinical or radiographic evidence of pancreatitis;
 - f) Grade 4 lymphopenia \leq 5 days in duration.
- Any dosing delay lasting > 6 weeks will be cause for permanent discontinuation. Extensions to the period of dose delays may be granted for individual subjects on a case by case basis after specific consultation and agreement between the Investigator and BMS Medical Monitor in settings where benefit/risk may justify continued study therapy (e.g., subject deriving clinical benefit who requires prolonged steroid taper for management of non-DLT irAEs, or experiences delays for management of a non-drug-related AE).
- Accordingly, dosing delays to allow for prolonged steroid tapers to manage drug-related AEs are allowed. Additionally, dosing delays > 6 weeks that occur for non-drug-related reasons may be allowed if approved by the BMS Medical Monitor.
- Prior to re-initiating treatment in a subject with a dosing delay lasting > 6 weeks, the BMS Medical Monitor must be consulted.
- Tumor assessments should continue as per protocol even if dosing is delayed.

All subjects who discontinue IP should comply with protocol specified follow-up procedures as outlined in [Section 3.3](#). The only exception to this requirement is when a subject withdraws consent for all study procedures including post-treatment study follow-up or loses the ability to consent freely (e.g., is imprisoned or involuntarily incarcerated for the treatment of either a psychiatric or physical illness).

If study treatment is discontinued prior to the subject's completion of the study, the reason for the discontinuation must be documented in the subject's medical records and entered on the appropriate CRF page.

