Patients on IV steroids may be switched to an equivalent dose of oral corticosteroids (e.g. prednisone) at start of tapering or earlier, once sustained clinical improvement is observed. Lower bioavailability of oral corticosteroids should be taken into account when switching to the equivalent dose of oral corticosteroids.

Hepatic Adverse Event Management Algorithm

Rule out non-inflammatory causes. If non-inflammatory cause, treat accordingly and continue I-O therapy. Consider imaging for obstruction.

[figure not shown]
Patients on IV steroids may be switched to an equivalent dose of oral corticosteroids (e.g. prednisone) at start of tapering or earlier, once sustained clinical improvement is observed. Lower bioavailability of oral corticosteroids should be taken into account when switching to the equivalent dose of oral corticosteroids.

*I-O therapy may be delayed rather than discontinued if AST/ALT ≤ 8 x ULN or T.bili ≤ 5 x ULN.

**The recommended starting dose for grade 4 hepatitis is 2 mg/kg/day methylprednisolone IV.

Endocrinopathy Management Algorithm

[figure not shown]
Rule out non-inflammatory causes. If non-inflammatory cause, treat accordingly and continue I-O therapy. Consider visual field testing, endocrinology consultation, and imaging.

Patients on IV steroids may be switched to an equivalent dose of oral corticosteroids (e.g. prednisone) at start of tapering or earlier, once sustained clinical improvement is observed. Lower bioavailability of oral corticosteroids should be taken into account when switching to the equivalent dose of oral corticosteroids.

Skin Adverse Event Management Algorithm

Rule out non-inflammatory causes. If non-inflammatory cause, treat accordingly and continue I-O therapy.

[figure not shown]
Patients on IV steroids may be switched to an equivalent dose of oral corticosteroids (e.g. prednisone) at start of tapering or earlier, once sustained clinical improvement is observed. Lower bioavailability of oral corticosteroids should be taken into account when switching to the equivalent dose of oral corticosteroids.

*Refer to NCI CTCAE v4 for term-specific grading criteria.

^If SJS/TEN is suspected, withhold I-O therapy and refer patient for specialized care for assessment and treatment. If SJS or TEN is diagnosed, permanently discontinue I-O therapy.

Neurological Adverse Event Management Algorithm

Rule out non-inflammatory causes. If non-inflammatory cause, treat accordingly and continue I-O therapy.

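### As printed, the Appendix 4 hepatic footnote allows delay for liver-injury DLTs that Section 4.3.6 says must end treatment (minor; exact reach depends on a flowchart box not shown)

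*Combined protocol and SAP*

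**What the plan says.** **The footnote.** In the Hepatic Adverse Event Management Algorithm of Appendix 4, an asterisked note reads "I-O therapy may be delayed rather than discontinued if AST/ALT" is no more than 8 x ULN or total bilirubin is no more than 5 x ULN. The note does not mention DLTs.

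**The hepatic DLT.** Section 4.3.1 A opens with "Any one of the following study drug-related events will be considered a hepatic DLT". One listed event is AST or ALT above 3 x ULN with concurrent total bilirubin above 2 x ULN and no initial sign of cholestasis, the Hy's-law pattern. The section adds: "Note that this special category of DLT uses ULN rather than CTC Grade for definition".

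**The stopping rule.** Section 4.3.6 requires permanent discontinuation of both study drugs. Its first trigger is "Any drug related AE occurring at any time that meets DLT criteria as outlined in" Section 4.3.1, subject to exceptions (a) to (f). Section 3.11 gives this mandatory force: "Subjects MUST discontinue investigational product (IP) (and non-IP at the discretion of the Investigator) for any of the following reasons", and the list includes "Protocol defined reasons for discontinuation", with a reference to Section 4.3.6.

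**Resumption.** Section 4.3.4 says "Subjects not meeting guidelines for permanent discontinuation will be permitted to resume therapy based on the criteria specified below in" Section 4.3.5. Section 4.3.5 opens by limiting resumption to drug-related AEs that are not DLTs.

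**Status of the algorithms.** Section 1.6 says AE treatment will follow institutional guidelines and the recommended algorithms, including those appended to the protocol. Section 4.3.2 recommends the Appendix 4 algorithms for this trial. The appendix describes itself as guidance to the investigator.

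**The concern.** A site handling a liver event is directed to Appendix 4 and finds there a printed permission to delay, with numerical limits that take in much of the Hy's-law range. The rule that removes this permission is in Section 4.3.6. The footnote does not point to it, and no clause says outright that Section 4.3.6 overrides the appendix. The hierarchy has to be inferred from several sections.

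At stake is the handling of a drug-related liver-injury DLT: a site may treat the event as a temporary hold when the protocol requires treatment to end. Liver events are relevant here. The clinical safety summary just before Section 1.5.5 reports a Grade 3 hepatic enzyme elevation, with no cause identified other than study drug, in a subject on the 800 mg/240 mg combination. Section 3.9.1 also admits hepatocellular carcinoma subjects with AST/ALT up to 5 x ULN. Such a subject may be above the 3 x ULN cut-off at entry, although a DLT would still require the bilirubin criterion and attribution to drug.

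**Working it through.** The plan states no figure to reproduce. The check asks whether the DLT region and the footnote region overlap. It uses only cut-offs printed in the protocol.

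**Inputs.** Let x = AST or ALT and y = total bilirubin, both in multiples of ULN. The event is drug-related, without cholestasis.

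- DLT (Section 4.3.1 A, ULN-based category): x > 3 and y > 2.
- Consequence (Section 4.3.6): permanent stop unless an exception applies. The exceptions cover (a) gastrointestinal events and abdominal pain, (b) pruritus or rash, (c) electrolytes, (d) neutropenia, (e) amylase or lipase, and (f) lymphopenia. Hepatic exceptions: 0 of 6.
- Footnote (Appendix 4) as printed: delay allowed if x ≤ 8 or y ≤ 5. Narrower reading: delay allowed only if x ≤ 8 and y ≤ 5.

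**Worked case.** x = 6, y = 2.5.

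1. 6 > 3 and 2.5 > 2, so this is a hepatic DLT.
2. No exception applies, so Section 4.3.6 requires a permanent stop.
3. 6 ≤ 8 and 2.5 ≤ 5, so the footnote allows delay under either reading.

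**Further cases.**

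| AST/ALT (x) | Bilirubin (y) | DLT, so permanent stop | Delay allowed, 'or' | Delay allowed, 'and' |
|---|---|---|---|---|
| 4 | 2.5 | yes | yes | yes |
| 6 | 3 | yes | yes | yes |
| 8 | 5 | yes | yes | yes |
| 8 | 12 | yes | yes | no |
| 15 | 3 | yes | yes | no |
| 25 | 4.9 | yes | yes | no |
| 9 | 5.1 | yes | no | no |

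**Result.** Under both readings the texts conflict wherever 3 < x ≤ 8 and 2 < y ≤ 5. Under the literal 'or', the footnote fails to reach a DLT of this kind only when x > 8 and y > 5 together. The conclusion uses only the first region, which does not depend on how 'or' is read.

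The grade-based hepatic DLTs (any Grade 3 or higher AST, ALT or bilirubin; symptomatic Grade 2 AST or ALT) are left out of the comparison, because the protocol does not give the CTCAE limits in ULN multiples.

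**Which text controls.** Section 4.3.6 is phrased as a requirement, Section 3.11 repeats it as an obligation, and Sections 4.3.4 and 4.3.5 make resumption depend on its criteria not being met. Appendix 4 is guidance. Section 3.6 adds little: it says a DLT "will lead to dose interruption and/or permanent discontinuation of study drug as defined in Section 4.3.6", which leaves interruption open.

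**The case against.** The case against has real weight.

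- **Restarting drug is already barred.** The footnote speaks only of delay. Section 4.3.5 allows dosing to resume after non-DLT AEs resolve, and it requires case-by-case review with the Medical Monitor for any AE with clinical risk. This stands. A reader might infer that the protocol lets a site resume both drugs after a liver-injury DLT; the documents do not support that.
- **Holding drug is not itself a fault.** Section 4.3.4 requires study drug to be held for any DLT. This stands: the defect is that the footnote offers delay as an alternative to stopping.
- **Roles are divided.** Section 4.3.4 leaves permanent stops to Section 4.3.6 and sends Grade 2 hepatic events to Appendix 4 for management. This mostly stands. However, symptomatic Grade 2 AST or ALT elevation is itself a hepatic DLT, so the division does not keep the appendix clear of DLTs.
- **The flowchart is not shown.** The box carrying the asterisk may limit the note or refer to the protocol's stopping criteria. This stands, and it means the absence of a DLT exclusion is established for the footnote text only. A reader might infer that the whole algorithm ignores DLTs; that cannot be shown.
- **The sponsor would know quickly.** Section 6.6 makes potential drug-induced liver injury reportable as an SAE, and Section 6.1.1 requires SAEs to be reported within 24 hours. This limits exposure but does not correct the printed permission.

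Calling the appendix guidance settles which text prevails. It does not make the text right, since Sections 1.6 and 4.3.2 send sites to it.

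**Conclusion.** The footnote is wrong as written, and the error is minor. For drug-related AST/ALT above 3 and up to 8 x ULN with bilirubin above 2 and up to 5 x ULN, without cholestasis, it prints a permission that the controlling Section 4.3.6 withholds. What remains after the safeguards is that a site following the footnote could delay treatment instead of permanently stopping it.

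The conclusion assumes that the event is judged drug-related and that the unseen box does not already exclude DLTs. No event frequency is claimed. No effect on dose escalation, DLT counting, any endpoint or any analysis is shown. Confidence is medium, because of the missing flowchart.

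**What to change.** Add at the Appendix 4 hepatic footnote: *This does not apply to any drug-related event meeting the hepatic DLT criteria in Section 4.3.1 A, including AST/ALT >3 x ULN with total bilirubin >2 x ULN without initial findings of cholestasis; Section 4.3.6 requires permanent discontinuation.* In Section 4.3.2, state that Section 4.3.6 takes precedence over Appendix 4.

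If the sponsor does intend delay for some hepatic DLTs, it should write an explicit hepatic exception into Section 4.3.6 so that the texts agree.

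The cost is one sentence and one cross-reference, with no added procedures or subjects.

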APPENDIX 5 CHILD-PUGH SCORE

Scoring

The score employs five clinical measures of liver disease. Each measure is scored 1-3, with 3 indicating most severe derangement.

Parameter	Points Assigned		
	1	2	3
Ascites	Absent	Slight	Moderate
Bilirubin (mg/dL)	≤ 2	2 to 3	> 3
Albumin (g/dL)	> 3.5	2.8 to 3.5	< 2.8
Prothrombin Time (seconds over control)	1-3	4 to 6	> 6
INR	< 1.7	1.8 to 2.3	> 2.3
Encephalopathy	None	Grade 1 to 2	Grade 3 to 4

Interpretation

Chronic liver disease is classified into Child-Pugh class A to C, employing the summation of score from above. These scores correlate with one and two year survival:

Points	Class	One year survival	Two year survival
5-6	A (well compensated disease)	100%	65%
7-9	B (significant functional compromise)	80%	60%
10-15	C (decompensated disease)	45%	35%

APPENDIX 6 REVISED PROTOCOL SUMMARY OF CHANGE HISTORY

Overall Rationale for the Revised Protocol 04, 22-Nov-2017

The significant change in revised protocol 04 is the extension of treatment with BMS 986156 and nivolumab for up to 2 years. Data suggest that 2 years of PD-1 checkpoint inhibitor treatment may be sufficient for long-term benefit.

Revisions apply to all participants enrolled as applicable.

Summary of key changes of Revised Protocol 04		
Section Number & Title	Description of Change	Brief Rationale
Section 3.1 Study Design and Duration Treatment Phase	Increased the number of maximum treatment cycles from 6 to 13.	This increases the number of cycles to support 2 year duration
Section 3.2 Treatment with additional cycles Beyond 24 weeks	After completion of 3 cycles (24 weeks), qualifying subjects may receive 3 additional cycles. Subjects completing 6 cycles (48 weeks) in CR, PR or SD may be eligible for an additional 7 cycles.	This increases the number of cycles to support 2 year duration of treatment
Figure 3.4.1	Updated Overall Schematic	This includes the number of possible additional cycles
Table 5.1-2 On treatment procedural Outline	Monitoring of vital signs can be decreased for patients from cycle 4-13 as long as the patient hasn't experienced an IRR	Safety data supports the decrease in monitoring for patients without IRR
Table 5.5.1-1 and Table 5.5 1-2	Addition of PK and ADA samples being obtained for the additional cycles	PK/immunogenicity data will support identification of anti-drug antibodies during retreatment
6.1.1 Serious Adverse Event Collection and Reporting	Updated section for collection and reporting SAE	Adjusted guidance for reporting of SAE data in cases where patients have initiated new anti-neoplastic therapy
6.2.1 Non-serious Adverse Event Collection and Reporting	Updated section for collection and reporting AE	Adjusted guidance for reporting of AE data in cases where patients have initiated new anti-neoplastic therapy

Summary of key changes of Revised Protocol 04		
Section Number & Title	Description of Change	Brief Rationale
8.4.3 Efficacy Analyses	Added analyses of PFSR at month 12 in the treatment of BMS-986156 and nivolumab	To assess whether the subjects remain progression free and survival during treatment extension period
All	Minor formatting and typographical corrections	Minor, therefore have not been summarized
